In the Division of Pediatric Dentistry the recommendations are to treat first molars with fissure sealants. Nevertheless, sometimes patients cannot afford or do not want the sealant treatment. In addition, anatomical conditions with tissue overgrowth on the distal side of the molar sometimes do not allow placing a sealant. These are potential situations for using the CO₂-laser to render the fissure enamel caries resistant. Thus the intended study does not interfere with the typical treatment.

The interventions - treatment groups

Each tooth of a molar pair in the same jaw will be randomly assigned to one of the 2 different treatments.

The study treatments are:

- 1) CO₂ 9.3 μm short pulsed laser rendering fissure areas more caries resistant (using proven laser settings) plus fluoride treatment (experimental group)
- 2) Fluoride treatment alone (control group)

- All study teeth will receive F-varnish application at baseline and every 6 months

Randomization of study teeth - allocation concealment

After enrollment subject's molars will be randomly assigned to the experimental or control group. The molar on the dominant side (right or left) will be randomly assigned to either the test or the control group with the non-dominant (contralateral) side receiving the other treatment. This is because dominant side determined by handedness may relate to oral hygiene.

A study independent person will create a randomization list, which will be created by a random number generator (QuickCalcs Online Random Numbers by GraphPad Software, Inc.).⁴⁶ The randomization list will be kept locked by a dental assistant (DA), group assignments will be in separate, closed opaque, sequentially numbered envelopes; only after

a subject has been enrolled the next-in-line group assignment will be revealed.

Blinding

The doctor performing the laser treatment and the dental assistant (DA) will not be blinded to subjects' group assignment and will explain the assignment to the subjects. The participant will also not be blind to the treatment. The DA will inform the laser treating doctor, which tooth will be the intervention and which the control tooth.

An independent study investigator will be blinded to subjects' group assignments. The DA will serve as the go-to person for subjects.

The statistician will be blinded to treatment assignment by (randomly) labeling the 2 groups as 0 and 1, without giving the statistician the key.

Study duration

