Eligibility criteria for participants

1. Inclusion Criteria

- age 6 or older, in good general health
- subject is of moderate or high caries risk according to CAMBRA
- has at least one pair of unsealed molars in at least one jaw with need for a sealant
- teeth with an ICDAS code 0, 1 and 2 with deep grooves and fissures providing an anatomical stick for an explorer
- willing to comply with all study procedures and protocols
- must be able to read and understand English
- have an understanding of the study
- residing in San Francisco or other nearby locales with community water fluoridation (to eliminate water fluoridation as a potential confounding variable)
- patient and parent/guardian able to provide written informed consent in English
- willing to sign the "Authorization for Release of Personal Health Information and Use of Personally Unidentified Study Data for Research" form; data will only be used for research.
- 2. Exclusion Criteria
- show evidence of extremely poor oral hygiene
- subjects suffering from systemic diseases, significant past or medical history with conditions that may affect oral health or oral flora (i.e. diabetes, HIV, heart conditions that require antibiotic prophylaxis),
- subjects with Nut Allergy
- taking medications that may affect the oral flora or salivary flow (e.g. antibiotic use in the past three months, drugs associated with dry mouth / xerostomia [extreme high caries risk])
- other conditions that may decrease the likelihood of adhering to study protocol
- subjects who will leave the area and are unable to complete the study

Sample size calculation & statistics

Sample size calculations are performed by UCSF Department of Epidemiology and Biostatistics using PASS 12 Power Analysis & Sample Size Software (http://www.ncss.com/software/pass/).

We assume that we will enroll into the suggested in-vivo occlusal caries prevention by short-pulsed CO_2 9.3 µm laser prospective, randomized, single blinded clinical study roughly 70 to 80 subjects.

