The primary analysis of this study will compare ICDAS scores for the laser group vs. controls. To this end, we will perform mixed effects proportional odds regression modeling with outcomes of ICDAS and SOPROLIFE scores. These models will explicitly account for within patient clustering and will include group (laser vs. control) as the main predictor along with tooth site and additional potential moderating variables such as age, sex, snack habit measures, tooth brushing habit, and dental history predictors. Importantly, we will include interactions of these additional predictors with the group predictor as well as time, which may indicate whether there is possible differential protectiveness of laser (over time) in specific subgroups. The models will be explored in a bottom up approach with each predictor considered in models one at a time along with group, group by predictor interaction and tooth site. If we see important effects, we will then combine a small number of predictors based on scientific plausibility in a single model, though we note that these will be far from definitive models given the sample size and scope of the proposed study. P \leq 0.05 will be considered statistically significant though we will emphasize that any model results are highly speculative and will require independent verification.

IRB approval

Investigational Review Board approval (UCSF Committee on Human Research CHR) will be achieved before the study will be started.

If requested the IRB can additionally scrutinize the study and will state that the study was conducted under the rules of GCP - Good Clinical Practice.

References

- [1] Chan, A. W., Tetzlaff, J. M., Altman, D. G., Laupacis, A., Gotzsche, P. C., Krleza-Jeric, K., Hrobjartsson, A., Mann, H., Dickersin, K., Berlin, J. A., Dore, C. J., Parulekar, W. R., Summerskill, W. S., Groves, T., Schulz, K. F., Sox, H. C., Rockhold, F. W., Rennie, D. and Moher, D., "SPIRIT 2013 statement: defining standard protocol items for clinical trials," Ann Intern Med 158(3), 200-207 (2013).
- [2] Schulz, K. F., Altman, D. G., Moher, D. and Group, C., "CONSORT 2010 Statement: updated guidelines for reporting parallel group randomized trials," Open medicine : a peer-reviewed, independent, open-access journal 4(1), e60-68 (2010).

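### Treatment is allocated by dominant side, but the primary model does not name dominant side; pre-specifying it as a fixed term removes chance imbalance at almost no cost

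*Combined protocol and SAP*

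**What the plan says.** The section on randomization of study teeth sets the unit of allocation: "The molar on the dominant side (right or left) will be randomly assigned to either the test or the control group", and the contralateral molar receives the other treatment. The reason follows directly: "This is because dominant side determined by handedness may relate to oral hygiene". On how the list is made, the section says: "A study independent person will create a randomization list, which will be created by a random number generator". Concealment is described too: "group assignments will be in separate, closed opaque, sequentially numbered envelopes". It does not say whether the list is blocked, balanced or unrestricted.

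The Data Analysis section specifies a mixed effects proportional odds model. On clustering: "These models will explicitly account for within patient clustering". On predictors, the model "will include group (laser vs. control) as the main predictor along with tooth site and additional potential moderating variables", with age, sex, snacking, brushing and dental history given as examples. Tooth site is not defined and dominant side is not named. The further predictors are to be tried one at a time and combined if they look important.

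The sample size section expects to enrol "roughly 70 to 80 subjects" and bases power on 50 after loss to follow-up, one molar pair each.

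**The concern.** In a split-mouth trial, side plays the part that period plays in a crossover: each participant receives both treatments, one in each position. The usual practice is to analyse by the factor used in the allocation. Here the plan singles out dominant side as possibly prognostic and allocates by it, but does not carry it into the model.

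The terms that are named do not clearly fill the gap. Age, sex and habits take the same value for both teeth of a patient, so they cannot absorb a difference between the two sides. Tooth site might mean left or right, which matches dominant side in right-handed participants and is reversed in left-handed ones. It might instead mean jaw or tooth type, which carries no side information.

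Two things are at stake. First, if side matters, an uneven split in the one trial that is run moves the estimate up or down. Second, if side is not named in advance, adjusting for it once an uneven split has been seen becomes a data-dependent choice, and the one-at-a-time approach to predictors leaves room for that.

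**Working it through.** **Inputs.** From the sample size section: 50 pairs, 75% discordant, difference in proportions 0.35, 5% level (taken as two-sided), McNemar test. Assumed: a side effect g, the difference between dominant and non-dominant side in the proportion worsening. The documents give no value, so 0 to 0.30 was examined. Also assumed for this check: an unrestricted list and one pair per subject.

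**1. The plan's own figure.** The number of discordant pairs is binomial(50, 0.75). Each favours laser with probability (0.75 + 0.35)/2 ÷ 0.75 = 0.733. Summing over these, the two-sided exact McNemar test has 79.8% power, so the stated 80% reproduces. The standard error of the paired difference is √[(0.75 − 0.35²)/50] = √(0.6275/50) = 0.112.

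**2. How uneven the split can be.** The number with laser on the dominant side is binomial(n, 0.5).

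| n | 95% limits | Share | Chance of 60/40 or worse |
|---|---|---|---|
| 50 | 18 to 32 | 36% to 64% | 0.203 |
| 80 | 31 to 49 | 39% to 61% | 0.093 |

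At n = 50, a split of 18/32 or more uneven in either direction has probability 0.065.

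**3. The shift this causes.** With k of n participants having laser on the dominant side, shift = g × (2k/n − 1).
- At the limit for n = 50, 2 × 32/50 − 1 = 0.28. The shift is 0.28 × 0.10 = 0.028 or 0.28 × 0.20 = 0.056.
- The SD of (2k/n − 1) is 1/√50 = 0.141. The typical shift is 0.141 × 0.10 = 0.014 or 0.141 × 0.20 = 0.028.
- At n = 70 and n = 80 the SD factor falls to 0.120 and 0.112.

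**4. Averaged over the randomisation.** With an unrestricted list, each pair has expected difference 0.35 + g or 0.35 − g with equal chance, which averages to 0.35 for any g. In 200,000 simulated trials per setting with side omitted, the mean estimate stayed at 0.35 and power at 79.6% to 79.8%. With no laser effect, type I error was 3.4% to 3.5% (exact test) or 4.8% to 4.9% (uncorrected) for every g.

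**5. Given the split that occurs** (side omitted, exact test, n = 50, true difference 0.35):

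| g | Power at 25/25 | Power at 18/32 | Power at 32/18 |
|---|---|---|---|
| 0.10 | 80% | 72% | 87% |
| 0.20 | 81% | 63% | 92% |

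With no laser effect, the exact test at an 18/32 split rejects 3.7% (g = 0.10) or 4.8% (g = 0.20) of the time. The uncorrected test rejects 5.3% or 6.6%. These rates apply only to such a split; step 4 gives the overall rates.

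**6. What adjusting for side gains on average.** The adjusted estimate is the mean of the two side-specific differences. Its SD over 200,000 simulated trials, against 0.112 unadjusted, is:
- g = 0: 0.113, a loss of about 1%
- g = 0.10: 0.112, no change
- g = 0.20: 0.110, a gain of about 2%
- g = 0.30: 0.105, a gain of about 6%

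**7. What balancing the list gains on average.** Forcing 25/25 with side omitted moves power from 79.6% to 80.1% (g = 0.10), 79.7% to 80.6% (g = 0.20) and 79.8% to 81.8% (g = 0.30).

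**The case against.** The strongest reply is that the sentence about handedness describes a safeguard. Randomising the treatment of the dominant side makes side independent of treatment, so a side effect of any size averages out of the laser comparison. Chance imbalance is ordinary sampling error, already covered by the standard error and the test. This stands. A reader might infer that a side effect remains in the laser estimate as a bias, or that the test is invalid. Neither follows from the design, and step 4 shows neither.

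Three other stronger readings also go beyond the text. The plan says side may relate to hygiene; it does not say an effect is expected, and gives no size. It does not say the list is unrestricted; it is silent. And it cannot be said outright that the model omits side, because tooth site is included and could carry left or right.

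It is also fair that the 0.03 to 0.06 shift is a tail case on an assumed input: a quarter to a half of one standard error, and small beside the planned difference of 0.35. The average gain from adjusting or balancing is slight.

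The objection does not remove the case for naming the term. The trial will have one split, visible before analysis. If it is uneven and side matters, the shift can be removed with information already needed to allocate. Deciding this in advance also takes away later discretion.

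**Conclusion.** The concern holds as a low-cost improvement in precision and pre-specification. It does not identify an error that invalidates the comparison. Dominant side is the within-patient factor the trial allocates by, and the primary model should name it.

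At 50 evaluable subjects and an assumed side effect of 0.10 to 0.20, the typical shift is 0.014 to 0.028, and 0.03 to 0.06 at the 95% limit of imbalance, against a standard error of about 0.11. At that limit, power could be about 72% or 63% in place of about 80% if the split is unfavourable, and higher than planned if it is favourable. If side has no effect, nothing is gained.

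These figures rest on the assumed side effect, an unrestricted list, one pair per subject and the binary McNemar metric that the plan uses for power. The proportional odds model was not simulated. That randomised side causes no systematic bias does not depend on the size of the side effect.

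**What to change.** In the Data Analysis section, pre-specify dominant side (yes/no for each tooth) as a fixed term in the primary model beside group and tooth site, as period is in a crossover. Record it for each study tooth with the allocation. In the same edit, define tooth site and state whether the randomisation list is restricted.

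Cost: one degree of freedom and no extra patients or visits, since dominant side must be known to allocate. If side has little or no effect, the precision loss is negligible (about 1% in the check above).

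Optional, and only if the envelopes are not yet prepared: have the independent person generate the list in permuted blocks of varying size, so that laser falls on the dominant side in about half of participants. This adds at most about 2 points of average power over the range examined, so the model term is the part that matters.

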The subjects will be recruited from the UCSF School of Dentistry. They will be recruited from the UCSF Predoctoral, Postgraduate Pediatric Dental and Postgraduate orthodontic clinics. The Pediatric Dentistry Clinic sees 200 to 300 patients in need of multiple fissure sealants per year. Approximately 2,500 sealants are placed every year. (There are reasons why sealants are not placed; these patients will be eligible for this study described here – see below.)

Subjects will be visiting the dental clinics for a new patient visit or a periodic oral exam. Subjects will have at least one pair of contralateral molars (first) in need of fissure sealants. Subjects will be treated in the Pediatric Dentistry and in the PRDS facilities.

Experimental Design

Enrollment, Consenting & Randomization: Flyers posted in the School of Dentistry will be

used to recruit patients and study investigators (and/or staff) will recruit their own patients directly in person (outside the direct treatment area).

When patients are seen by their dentist and the treating dentist believes that the patient might fit into the study, he/she will ask the potential participant (and parent/guardian for minors) whether she/he might be interested in being in a dental study. If the subject is interested the treating dentist will ask the potential participant (and parent/guardian for minors) whether she/he gives permission to disclose her/his name to the researchers. If the patient agrees (and parent/guardian for minors), a Clinical Investigator ([name], [name]) and/or the Clinical Study Coordinator ([name]) will ask the potential subject whether she/he is interested in participating in this study. If so the Clinical Investigator/Clinical Study Coordinator will explain the whole study and will further check for eligibility.

Consenting all study subjects and their parents/guardians will take place prior to entering the study. Potential participants will be consented and enrolled by the PI/I, and a senior research associate, respectively.

To achieve adequate participant enrolment to reach targeted sample size, advertisements will be placed in the Pediatric Dentistry Clinic area as well as in other patient areas of the School of Dentistry.

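### Keeping the full randomization list with the unblinded dental assistant is an avoidable weakness in allocation concealment

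*Combined protocol and SAP*

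**What the plan says.** Under Randomization of study teeth - allocation concealment, the protocol sets up three safeguards. First, "A study independent person will create a randomization list". Second, "group assignments will be in separate, closed opaque, sequentially numbered envelopes". Third, disclosure is sequential and comes only after "a subject has been enrolled the next-in-line group assignment will be revealed". The same paragraph names the custodian of the list: "The randomization list will be kept locked by a dental assistant (DA". It does not say who holds the envelopes.

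The Blinding section describes the assistant's other duties. "The doctor performing the laser treatment and the dental assistant (DA) will not be blinded to subjects' group assignment", and both explain the allocation to the subject. "The DA will inform the laser treating doctor, which tooth will be the intervention and which the control tooth". Finally, "The DA will serve as the go-to person for subjects".

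Under Experimental Design, consent and enrolment belong to the investigators and a senior research associate. Explaining the study and checking eligibility belong to a clinical investigator or the study coordinator. Recruitment is drawn more widely: "study investigators (and/or staff) will recruit their own patients directly in person", with a note that this takes place away from the treatment area. The assistant is not named in any of these steps and is not excluded from them.

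**The concern.** Sealed envelopes protect future assignments only as long as nobody involved in the trial can read the sequence another way. Here one team member can look up any later entry without opening an envelope, and the only stated barrier is a lock that the same person keeps. The independence gained by having an outsider generate the list is given up at the next step.

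What is randomized is the side: whether the molar on the dominant side is lased or serves as control. Someone who knows the next entry cannot send a healthier patient to one arm, but could influence which pairs enter. If the next entry makes the dominant side the control, a patient whose dominant-side molar looks worse could be taken now, and a patient with the opposite pattern deferred. A paired analysis does not remove the resulting imbalance, because it lies within the pair.

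**Working it through.** The point rests on who holds and who acts on the allocation. The arithmetic at the end only illustrates scale.

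**Step 1. Roles side by side.**

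| Step | Role named in the plan |
|---|---|
| Generates the list | Study-independent person |
| Keeps the list | Dental assistant, under lock |
| Holds the envelopes | Not stated |
| Recruits | Treating dentists, investigators and/or staff |
| Checks eligibility | Clinical investigator or study coordinator |
| Consents and enrols | Investigator and senior research associate |
| Tells the laser doctor and subject the allocation | Dental assistant (the doctor also explains it to the subject) |
| Subjects' contact | Dental assistant |
| Scores at baseline | Dentist blinded to group, before treatment |

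The list and the enrolment decision sit with different people. Foreknowledge affects enrolment only if it passes from the assistant to those who enrol, or if the assistant has an unstated part in recruitment or pair selection.

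**Step 2. Is there anything to select on?** The Subjects section and the inclusion criteria admit molars with ICDAS 0, 1 or 2, and no rule requires the two molars of a pair to have the same code. Since the code is an entry criterion, someone must assess it before enrolment. The Clinical Study section places the blinded baseline examination before treatment. The plan does not require pair, dominant side and baseline scores to be recorded before the envelope is opened.

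**Step 3. Direction.** Two primary outcomes are listed.
- *Occurrence of ICDAS 3.* A tooth at code 2 is 3 - 2 = 1 step from the event; a tooth at code 0 is 3 - 0 = 3 steps. Putting the worse molar in control would tend to favour laser. The Data Analysis section does not name baseline ICDAS among its covariates.
- *Change in ICDAS.* A tooth with a higher baseline score may progress faster, but with scoring error it also tends to regress downward, which would favour control. The direction is uncertain.

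**Step 4. Illustration of scale.** The documents give no figure for steering, so two quantities are assumed: the share s of pairs steered, and the gap g in worsening risk between the two molars of a steered pair. From the sample size section come n = 50 pairs, the McNemar test, 75% discordance and the detectable difference of 0.35. The plan's own power statement reproduces: exact McNemar power for these inputs is 79.8%, against the stated 80%. A discordance of 50% is added as a second assumed value.

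With no true laser effect, the spurious difference is d = s × g, the shift is d / √(discordance / 50), and the two-sided asymptotic type I error is P(Z > 1.96 - shift) + P(Z < -1.96 - shift).

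| s, g | d | Discordance | Shift | Asymptotic | Exact test |
|---|---|---|---|---|---|
| none | 0 | 0.50 / 0.75 | 0 | 5.0% | about 3% |
| 20%, 0.2 | 0.04 | 0.50 | 0.40 | 6.9% | 4.3% |
| 20%, 0.2 | 0.04 | 0.75 | 0.33 | 6.2% | 4.3% |
| 40%, 0.3 | 0.12 | 0.50 | 1.20 | 22.4% | 16.3% |
| 40%, 0.3 | 0.12 | 0.75 | 0.98 | 16.5% | 12.7% |

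With the exact test, which is the version that matches the plan's power figure, mild steering stays below the nominal 5%. Only the heavy scenario, whose d is 0.12 / 0.35 = 34% of the detectable difference, does visible damage. McNemar is the plan's sample-size surrogate; the primary analysis is a mixed proportional-odds model, so these figures do not carry over directly.

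**The case against.** A reader might infer that the envelopes conceal nothing from the clinical team, or that concealment fails outright. The documents do not support that. The list is kept locked, disclosure follows enrolment, and other roles check eligibility, consent and enrol. The laser doctor has to be told the allocation by the assistant, so is not described as having the list. Nothing says that the assistant works alongside those who enrol, and in-person recruitment is placed outside the treatment area. Reading the assistant into the word staff is a guess.

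The room for steering is also narrow. Every subject receives both treatments, so patient-level selection between arms is impossible. Dominant side is set by handedness and is not a label to be chosen freely. Study teeth are described as contralateral first molars, so at most an upper and a lower pair are available, and some subjects are expected to contribute more than one pair. Steering needs knowledge of both the list and the tooth scores. A blinded dentist makes the baseline assessments.

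Most of this stands, and it limits the harm. It does not answer the custody question. The plan does not keep the assistant out of recruitment or pair selection, and blinded scoring records an imbalance created by selection but does not prevent it. It is also true that the assistant would still hold the sealed envelopes after the fix. The gain is that an unrecorded look at the whole sequence is replaced by envelopes on which tampering would show.

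**Conclusion.** The point holds as an avoidable weakness in concealment. It is not evidence that concealment has failed or that anyone steered allocations. It matters only if the assistant consults the list and acts on it or passes it on, or has a part in recruitment or pair selection; the plan is silent on both. Any bias would be at side level, among pairs whose molars differ in baseline ICDAS. It would tend to favour laser on ICDAS 3 occurrence, with no clear direction for change in ICDAS. Its size cannot be derived from the documents: the type I error figures above depend on assumed values of s and g and on a surrogate test, and with no steering there is no effect. Sample size and power are untouched. The case for acting is that a stated rule can be changed at almost no cost to close a route to foreknowledge.

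**What to change.** Replace the custody sentence under Randomization of study teeth - allocation concealment. The study-independent person who generates the list should also prepare the sealed envelopes and keep the list, with no access for the dental assistant, the treating doctor or anyone who recruits, enrols or scores subjects. The assistant should hold only the sealed, sequentially numbered envelopes. The next one should be opened, dated and logged against the subject number once eligibility, study pair or pairs, dominant side and baseline scores have been recorded. The list can then be reconciled with the envelope log at the end of the study.

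The cost is a few sentences of protocol text and a change of custodian. The independent person already exists, and visits, sample size and analysis stay as they are. The one drawback is that this person must be reachable if an envelope is lost. If enrolment is already complete, the sponsor can instead document who had access to the list and report within-pair baseline ICDAS codes by treatment.

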The clinical study presented here will show that using a $CO_2 9.3 \mu m$ short pulsed laser irradiation markedly inhibits caries progression in pits and fissures in comparison to fluoride varnish alone over 12 months.

Study Design

[x]Randomized []Investigational intervention without random assignment

[x]Blinded, Single, []Blinded, Double

[x]Prospective [x]Control []Behavioral

Study's formal designation:

[]Phase I [x]Phase II []Phase III []Phase IV

Framework:

[x] superiority [] equivalence [] non inferiority [] exploratory

Study type

The CHR application will be a minimal risk, full committee review application.

Methodology

Specific Aims

A) The aim of the study is to assess if the use of the new CO₂ - 9.3µm short-pulsed laser in addition to fluoride therapy allows rendering occlusal pit and fissures caries resistant in comparison to fluoride therapy alone in participants in a randomized, single blind, prospective, split mouth controlled, clinical trial. The fissure mineral loss will be quantified by visual exams with the International Caries Detection and Assessment System (ICDAS II), SOPROLIFE daylight and blue fluorescence, and by DIAGNOdent Laser Light-induced Fluorescence.

Primary study outcome measures

Differences in change in ICDAS scores between matched case and control teeth (within patient) from baseline to 6 months and baseline to 12 months

Differences in occurrence of ICDAS 3 scores between matched case and control teeth (within patient) from baseline to 6 months and baseline to 12 months

Secondary study outcome measures

Differences in change in SOPROlife scores between matched case and control teeth (within patient) from baseline to 6 months and baseline to 12 month

Material & Methods

Clinical Study:

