Power calculations below are based on results obtained from our pilot study on caries prevention ⁵¹ ([name], P., et al, "In-vivo occlusal caries prevention by pulsed CO₂ -laser and fluoride varnish treatment - a clinical pilot study," Lasers in Surgery and Medicine 45(5), 302-310 (2013)). For the purpose of sample size calculation, we assume a simple measure based on our primary endpoint of change in ICDAS scores with only one pair of molars per subject, by comparing the proportion of teeth with worsening ICDAS score in laser vs. control groups. (We actually expect some subjects to provide more than one pair of molars, which will add to the power.) Note that we will actually use a generalized linear mixed model (proportional odds) for the primary analysis based on differences in scores, but there are no general power analysis software procedures for that test. Therefore, we use this simpler and less powerful metric to conservatively guide power considerations. In the pilot study we observed 1 participant with worsening ICDAS score in the laser group vs. 9 participants in the control group. We determine power based on a McNemar test to account for the pairing of observations. The observed difference in ratio for worsening ICDAS score was 0.56 (0.06 laser vs. 0.62 control). With a conservative sample size of 50 (after loss to follow up) and assuming the same proportion of discordant pairs (75%), we would have 80% power to detect a difference in proportions of 0.35 at the 5% significance level (i.e. allowing for over 35% reduction in the pilot observed difference of 0.56). Furthermore, we expect to improve power further by working with the actual ICDAS scores and using the Wilcoxon signed-rank test (the extra power comes from being able to capture the extent of worsening in each case).

Data Analysis - by UCSF Department of Epidemiology and Biostatistics.

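### The primary ICDAS endpoint is change from baseline, but the analysis section models ICDAS scores and gives baseline ICDAS no fixed place in the model; the cost is precision, not bias

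*Combined protocol and SAP*

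**What the plan says.** All places are in section 2 (Synopsis) of the combined protocol and SAP.

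- **Primary study outcome measures**: the first outcome is "Differences in change in ICDAS scores between matched case and control teeth (within patient) from baseline to 6 months and baseline to 12 months".
- **Sample size calculation & statistics**: change in ICDAS is called the primary endpoint, and "we will actually use a generalized linear mixed model (proportional odds) for the primary analysis based on differences in scores". The same paragraph adds that "we expect to improve power further by working with the actual ICDAS scores and using the Wilcoxon signed-rank test".
- **Data Analysis**: "The primary analysis of this study will compare ICDAS scores for the laser group vs. controls". The model is a mixed-effects proportional-odds regression with ICDAS and SOPROLIFE scores as outcomes. "These models will explicitly account for within patient clustering and will include group (laser vs. control) as the main predictor along with tooth site". Age, sex, snacking, brushing and dental history follow as examples of possible moderators, with "each predictor considered in models one at a time along with group, group by predictor interaction and tooth site". Interactions with time are mentioned. Change, baseline ICDAS and a primary group-by-time contrast are not.
- **Subjects** and **Inclusion Criteria**: teeth with ICDAS 0, 1 or 2 are eligible. Neither section requires the two teeth of a pair to share a code.
- **Randomization of study teeth**: allocation is within the pair, by dominant side and not by baseline code.

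**The concern.** The endpoint is a change, while the model outcome reads as a score. If both teeth of every pair started at the same code, the paired contrast would be the same either way. The eligibility rules allow unequal codes, so two analysts following the plan could fit different primary models and obtain different p-values.

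On either reading, the starting code of each tooth is not used as a fixed covariate. The moderator list is open-ended, but its members are tried one at a time, so a baseline term added there would be exploratory. At stake is the precision of the primary comparison with about 50 pairs.

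**Working it through.** **1. The plan's own figure.** Inputs from the sample size section: 50 pairs, 75% discordant, difference 0.35, 5% level. The discordant cells are (0.75 + 0.35)/2 = 0.55 and (0.75 − 0.35)/2 = 0.20. Exact two-sided McNemar power, averaged over a Binomial(50, 0.75) number of discordant pairs, is 79.8%. This agrees with the statement that "we would have 80% power to detect a difference in proportions of 0.35 at the 5% significance level". That test is on worsening, which is already a change measure, so the figure is not altered by this point. It also says nothing about an analysis of raw follow-up scores.

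**2. Precision in the linear paired case.** Take the within-pair difference (laser minus control). Let its follow-up variance be 1, its baseline variance also 1, and let ρ be the within-tooth correlation beyond the patient effect. The documents give no ρ, so 0.2, 0.5 and 0.7 are assumptions.

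- Change: variance 1 + 1 − 2ρ = 2(1 − ρ)
- Raw follow-up: variance 1
- Baseline-adjusted: variance 1 − ρ²
- Ratio of adjusted to change: (1 − ρ²)/[2(1 − ρ)] = (1 + ρ)/2

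| ρ | Change | Raw | Adjusted | Width vs change | Width vs raw |
|---|---|---|---|---|---|
| 0.2 | 1.60 | 1 | 0.96 | √0.60 = 77% | √0.96 = 98% |
| 0.5 | 1.00 | 1 | 0.75 | √0.75 = 87% | √0.75 = 87% |
| 0.7 | 0.60 | 1 | 0.51 | √0.85 = 92% | √0.51 = 71% |

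The ordering does not need equal variances. If the baseline SD is k times the follow-up SD, change has variance 1 + k² − 2ρk. This exceeds 1 − ρ² by (k − ρ)², which is never negative. Adjustment is therefore never worse than either alternative, apart from the small cost of estimating a slope. It gains nothing over change when k = ρ.

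**3. An illustration at that favourable end for change.** Simulated follow-up codes were baseline plus an independent change (50 pairs, SD of change 0.65, nominal shift 0.5, codes limited to 0–3; all assumptions). With 0/25/50/75% of pairs starting one code apart, power was about 91/84/77/71% on raw scores and about 91% throughout on both change and adjusted. When all pairs start level, the choice is immaterial.

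**4. Which correlation fits the pilot?** The Background gives 12-month standard errors of change of 0.15 (laser) and 0.17 (control). With about 16 pairs (1/0.06), the SDs are 0.15 × 4 = 0.60 and 0.17 × 4 = 0.68. With 20 pairs they are 0.67 and 0.76. An ordinal simulation with control worsening set to the pilot's 0.62 and patient SD 1 logit gave SDs of change of roughly 0.8–1.1 at ρ of 0.2 and 0.5, and about 0.75–0.83 at 0.7. Only the 0.7 setting approaches the pilot.

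**5. Power at ρ = 0.7.** With exits at code 3 carried forward and an assumed effect of 1.4 logits, simulated power was 67.3% adjusted, 65.9% change and 49.2% raw. The 1.4-point gain over change is within Monte Carlo error (standard error up to 1.6 points). Without exits, the adjusted test rejected 6.8% of the time under the null, against 6.0% for change. No power gain over change is shown here; the gain over raw follow-up is 18.1 points.

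**The case against.** The strongest reply is that the conflict is thin. The outcome section defines an outcome, not an analysis. The sample size section itself uses scores loosely when it means the extent of worsening, so the analysis section may simply be shorthand for change. That is plausible, but the operative text still does not say so, and on the change reading baseline remains unadjusted.

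A second reply is that Data Analysis mentions time. If baseline is one of the time points and group-by-time is the contrast, change is captured and baseline enters as data. The text does not exclude this reading, but does not state it: time appears only in interactions used to look for differential effects in subgroups.

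Third, paired change under within-pair randomisation is a valid analysis. This stands. A reader might infer that leaving baseline out biases the laser effect, but the randomisation does not support that.

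Fourth, a reader might infer a large loss of power against change. Simulated gains of 13 and 10 points do appear at correlations of 0.2 and 0.5. Those settings do not match the pilot's spread of change, they give about 52–56% discordant pairs against the plan's 75%, and they use an assumed effect (62% vs about 40% worsening) smaller than the plan's 0.35 target. They should not be relied on.

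**Conclusion.** The point holds as one of definition and precision. The plan does not settle whether change or follow-up score is analysed, and baseline ICDAS is not a fixed term. A baseline-adjusted comparison is at least as precise as either. The gain over change is probably small, about 8% in interval width at the correlation closest to the pilot. The gain over raw follow-up is larger, about 29% in width at that correlation. These sizes rest on assumed correlations, equal variances at the two times, a linear approximation to an ordinal model, and pairs that do differ at baseline; the documents do not say how often they will.

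A reader might also infer an inflated type I error from repeated visits or several pairs per subject. That would require a joint model with a patient intercept alone. The plan says only that within-patient clustering will be accounted for, so the claim is not supported.

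**What to change.** In Data Analysis, state that the primary proportional-odds model, at each of the two visits named in the outcome section, has the follow-up ICDAS code as outcome and the tooth's baseline ICDAS code as a fixed covariate, outside the one-at-a-time moderator list. Specify the pre-laser reading, because Testing times lists baseline examinations both before and after laser treatment. In Primary study outcome measures and in the sample size section, add that this baseline-adjusted comparison is how change in ICDAS is assessed.

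If the visits, or several pairs from one subject, are modelled jointly, use patient-clustered robust standard errors or a random intercept for tooth within patient.

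The cost is wording in three places. The data are already collected. The downside is one extra parameter (baseline as linear) or two (as categories), with a small risk of non-convergence at about 50 pairs. Mean change can still be reported descriptively for comparison with the pilot.
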